17.1 Sample size calculation

This is a superiority trial comparing liraglutide to placebo. Superiority will be claimed if the p-value is less than 5% and the treatment favours liraglutide.

It is anticipated that the effect of liraglutide in adolescents with obesity will be similar to the effect observed in adults. The anticipated treatment difference for BMI SDS³³ is based on the results from trial NN8022 1839 in adults with overweight and obesity. For the sample size scenarios, treatment differences of -0.24, -0.26, and -0.28 were investigated.

The standard deviation (SD) is assessed based on publications by Reinehr et al. 2009¹³ Berkowitz et al. 2003⁵⁶ and trial NN8022-3967 in adolescents with obesity aged 12–17 years. For the sample size scenarios, SD of 0.25, 0.35 and 0.45 were investigated.

The effect of withdrawals on the analysis is accounted for as a reduction of the anticipated treatment difference and increase of the SD. Since a conservative imputation method is planned for the main analysis of the primary endpoint, it is assumed that withdrawn subjects respond as if treated with placebo for the entire trial. The assumed withdrawal percentage for this paediatric trial is 40% at week 56. A higher withdrawal percentage is assumed for this trial than what was seen in trial NN8022-1839 in adults, because this trial will include an adolescent trial population.

The total number of subjects is shown for the investigated scenarios in [Table 17–1](#) for 90% and 99% power.

Table 17–1 Sample size calculations for different scenarios with total number of randomised subjects

POWER	Treatment difference (completers)	SD		
		0.25	0.35	0.45
90%	-0.24	144	266	428
	-0.26	124	228	366
	-0.28	110	200	318
99%	-0.24	248	462	746
	-0.26	216	398	638
	-0.28	190	346	554

Based on the above mentioned references, it seems realistic and conservative to assume an SD of 0.35 and a treatment difference of –0.26. The minimum requirement in the Paediatric Investigation Plan is 154 randomised subjects while FDA requires a minimum of 100 subjects exposed to liraglutide. A sample size of 228 randomised subjects gives a power of 90%. Thus, the number of randomised subjects should be 228.

17.2 Definitions of analysis sets

The following analysis sets are defined in accordance with the ICH E9⁵⁷.

FAS: includes all randomised subjects who have received at least one dose of trial product and have any post-randomisation data. The statistical evaluation of the FAS will follow the intention-to-treat (ITT) principle and subjects will contribute to the evaluation “as randomised”.

SAS: includes all subjects exposed to at least one dose of trial product. Subjects in the SAS will contribute to the evaluation “as treated”.

Data from nominal visits (V19x, V25x and V30x) will be used prior to imputation of remaining missing data unless otherwise stated. For AEs, summaries will be presented separately for the periods “run-in”, “in-trial” and “on-treatment”, as defined in Section [17.4.1.2](#).

Before data are locked for statistical analysis, a blinded review of all data will take place. Any decision to exclude a subject or single observations from the statistical analysis is the joint responsibility of the Novo Nordisk trial statistician, the international trial manager and the international medical specialist. Exclusion of data from analyses will be used restrictively and normally no data should be excluded from the FAS. The subjects or observations to be excluded, and the reasons for their exclusion must be documented and signed by those responsible before database lock. The subjects and observations excluded from analysis sets, and the reason for this, will be described in the clinical trial report.

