9.5 Auxiliary supplies

The following will be provided by Novo Nordisk in accordance with the TMM:

- Direction for use for PDS290 pen-injector for trial product
- Needles for the device (maximum length to be used is 8 mm)
- BG meters and BG-meter auxiliary supplies

Only needles provided by Novo Nordisk must be used for administration of trial product.

10 Interactive web response system

A trial-specific IWRS will be set up which can be accessed at any time via the internet or telephone. Access to the IWRS must be restricted to and controlled by authorised persons.

IWRS is used for:

- Screening
- Screening failure
- Randomisation
- Medication arrival
- Dispensing
- Treatment discontinuation
- Completion
- Code break
- Drug accountability
- Data change

IWRS user manuals will be provided to each trial site.

11 Randomisation procedure and breaking of blinded codes

At randomisation, the subjects will be randomised to one of two parallel treatment groups: liraglutide 3.0 mg or placebo. The randomisation will be carried out in a 1:1 manner using the IWRS.

The randomisation will be stratified according to pubertal and glycaemic status (see Sections [5.2](#)). Stratification will be controlled by the IWRS. The strata are:

Table 11–1 Strata

Tanner 2 or 3	Dysglycaemia yes
Tanner 2 or 3	Dysglycaemia no
Tanner 4 or 5	Dysglycaemia yes
Tanner 4 or 5	Dysglycaemia no

Dysglycaemia is defined as T2DM or pre-diabetes with FPG ≥ 5.6 mmol/L (≥ 100 mg/dL) and/or HbA_{1c} $\geq 5.7\%$ (see [Table 5–1](#)). The laboratory results from V8 must be used for this purpose.

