The subject and any biological material obtained from the subject will be identified by subject number and trial ID. Appropriate measures such as encryption or leaving out certain identifiers will be enforced to protect the identity of subjects in all presentations and publications as required by local, regional and national requirements.

16 Computerised systems

Novo Nordisk will capture and process clinical data using computerised systems that are described in Novo Nordisk Standard Operating Procedures and IT architecture documentation. The use and control of these systems are documented.

Investigators working on the trial may use their own electronic systems to capture source data.

17 Statistical considerations

If necessary, a statistical analysis plan (SAP) may be written in addition to the protocol, including a more technical and detailed elaboration of the statistical analyses. The SAP will be finalised before database lock.

Results from the statistical analysis will generally be presented by two-sided confidence intervals (CIs) with a confidence level of 95%. Superiority will be claimed if the two-sided p-value is less than 5% and the treatment estimate favours liraglutide.

The full analysis set (FAS) will be used in the analysis of the efficacy endpoints. For the safety endpoints, the safety analysis set (SAS) will be used. The definition of the analysis sets are given in Section [17.2](#).

Laboratory values below the lower limit of quantification (LLOQ) will be set to $\frac{1}{2}$ LLOQ.

The baseline value will be defined as the last measured and available value from randomisation (V9) and end of run-in (V8), if not otherwise specified.

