- For each of the 100 copies of the dataset, the estimated parameters and their variances from this model will be used to impute missing values at 56 weeks for subjects in both treatment arms, based on their factor levels and the values of the covariates.
- For each of the 100 complete datasets, the change from baseline in BMI SDS at 56 weeks will be analysed using the main ANCOVA model with treatment, sex, region, baseline glycaemic category, stratification factor for Tanner stage and interaction between baseline glycaemic category and stratification factor for Tanner stage as fixed effects, and baseline BMI SDS and baseline age as covariates.
- The estimates and SDs for the 100 data sets are pooled to one estimate and associated SD using Rubin's formula:

$$m_{MI} = \frac{1}{100} \sum_{i=1}^{100} m_i, SD_{MI} = \sqrt{\frac{1}{100} \sum_{i=1}^{100} SD_i^2 + \left(1 + \frac{1}{100}\right) \left(\frac{1}{100-1}\right) \sum_{i=1}^{100} (m_i - m_{MI})^2},$$

where m_i and SD_i are the estimated means and SDs for the 100 copies of the dataset, and m_{MI} , SD_{MI} are the pooled estimates. From m_{MI} and SD_{MI} , the 95% CI for the treatment difference and the associated p-value will be calculated.

The MI method does not assume missing at random. It assumes that withdrawn subjects in the placebo arm have a response similar to the completers in the placebo arm given similar baseline characteristics. In the active arm, the assumption is that withdrawn subjects behave as if they have been in the placebo arm during the entire trial regardless of the time of their withdrawal. In this way the assumptions are differential and conservative for estimating the treatment effect. The estimate in the primary analysis can be said to be an ITT estimator or an effectiveness estimand of the add-on effect of liraglutide to healthy nutrition and physical activity counselling.

Sensitivity analysis

To investigate the sensitivity of the results of the main analysis of the primary endpoint with regard to the handling of missing data, the following sensitivity analysis will be performed:

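### The FAS leaves out randomised subjects with no post-randomisation data, although it is labelled ITT and the primary imputation needs only baseline values; the effect is probably very small and easily removed

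*Protocol*

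**What the plan says.** Protocol 17.2 states that the FAS "includes all randomised subjects who have received at least one dose of trial product and have any post-randomisation data". SAP 2.1 repeats this unchanged. The opening of protocol section 17 and of SAP section 2 make the FAS the set for efficacy, and SAP Table 2-4 assigns it to the primary endpoint. Protocol 17.2 places the FAS under the ITT principle, and protocol 17.3 says of the result: "The estimate in the primary analysis can be said to be an ITT estimator".

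Protocol 17.3 fits the imputation model to placebo completers. Its terms are sex, region, glycaemic category, Tanner stratum and the interaction of the last two, with baseline BMI SDS, waist circumference, age and HbA1c. SAP Table 2-3 lists the same terms. The fitted model then imputes week 56 in both arms. For the active arm, protocol 17.3 assumes that withdrawn subjects respond as if on placebo throughout, however early they left.

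On sample size, protocol 17.1 says: "The assumed withdrawal percentage for this paediatric trial is 40% at week 56". It adds: "The effect of withdrawals on the analysis is accounted for as a reduction of the anticipated treatment difference and increase of the SD".

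The four sensitivity analyses (protocol 17.3, SAP 2.2.1) are LOCF, BOCF, completers only and MMRM. None brings back subjects who are outside the FAS.

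**The concern.** Whether a subject has any data after randomisation is itself a post-randomisation outcome, and treatment can influence it. Protocol 18.1 places the onset of gastrointestinal events with liraglutide 3.0 mg in weeks 1 to 4, and protocol 5.2 expects high attrition. A subject who takes the first dose, feels unwell and breaks off all contact without reporting anything would leave the primary analysis.

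Such a rule is usually justified because the analysis cannot use a subject without follow-up. That reason does not apply to this primary analysis, which imputes from baseline values alone. In the liraglutide arm, the subjects removed are ones the plan would otherwise count as placebo-like. Removing them raises the share of the arm credited with a drug effect, which works against the conservatism that protocol 17.3 claims. At stake is the match between the stated estimand and the population analysed. The size of the estimate is affected only slightly.

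**Working it through.** **1. Inputs**

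- Test: "Superiority will be claimed if the two-sided p-value is less than 5% and the treatment estimate favours liraglutide" (protocol section 17, opening).
- Allocation: "The randomisation will be carried out in a 1:1 manner using the IWRS" (protocol section 11).
- Effect and SD: "it seems realistic and conservative to assume an SD of 0.35 and a treatment difference of" -0.26 (protocol 17.1; the difference is for completers).
- Withdrawal: 40%, counted as a placebo response (protocol 17.1).
- Stated result: "A sample size of 228 randomised subjects gives a power of 90"% (protocol 17.1).
- Number of randomised subjects without post-randomisation data: not given. The counts used below are assumptions.

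**2. Reproducing the planned sample size**

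- Diluted effect: 0.26 × (1 - 0.4) = 0.156.
- Liraglutide variance, as a mixture of completers and placebo-like withdrawals: 0.35² + 0.4 × 0.6 × 0.26² = 0.1225 + 0.0162 = 0.1387.
- Placebo variance: 0.35² = 0.1225.
- Two-sample t calculation, two-sided 5%, 90% power: 114 per arm, 228 in total, with power 90.06%.

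This matches the stated 228, and the same method reproduces all 18 cells of Table 17–1. So 228 rests on every randomised withdrawal staying in the analysis as a placebo responder.

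**3. Standard error of the difference**

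√(0.1387/114 + 0.1225/114) = √(0.2612/114) ≈ 0.048.

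**4. Effect of the exclusion**

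Of 114 liraglutide subjects, 0.6 × 114 = 68.4 are expected to keep the effect of -0.26, and 45.6 are placebo-like. Excluding k of the placebo-like subjects leaves the numerator at 68.4 × 0.26 = 17.784 and cuts the denominator to 114 - k. The expected difference is therefore -17.784/(114 - k), which equals -0.156 × 114/(114 - k).

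| k excluded (assumed) | Expected difference | Relative change | Shift as share of SE |
|---|---|---|---|
| 0 | -0.156 | none | none |
| 1 | -0.157 | +0.9% | 0.0014/0.048, about 3% |
| 2 | -0.159 | +1.8% | 0.0028/0.048, about 6% |
| 5 | -0.163 | +4.6% | 0.0072/0.048, about 15% |

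Placebo exclusions do not move the expected difference. Protocol 17.3 assumes that placebo withdrawals resemble placebo completers with the same baseline characteristics, so removing some of them leaves the placebo mean where it was. With 5 placebo subjects removed and none on liraglutide, the difference stays at -0.156 and power is 89.4%.

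**5. Can the existing method take these subjects?**

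Yes. Imputation needs only baseline factor levels and covariates. SAP 2.3.2 fits the model to placebo subjects with BMI SDS at baseline and week 56, so subjects without follow-up never enter the fit, and adding them to the FAS leaves the imputation model unchanged. SAP Table 2-2 already has a category for them: non-retrieved drop-outs (MD).

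**The case against.** The strongest case is that the affected group is almost empty. The condition asks for data of any kind, not for a BMI SDS. One adverse event report or one visit value is enough. The first dose is injected on site (protocol 8.1.7), visits are weekly from V10 to V13 (8.1.8.1), and subjects are asked about adverse events at every contact (12.2). Early intolerance that is reported keeps the subject in the FAS. Even after withdrawal, an end-of-trial form and final drug accountability are required (8.1.9), although the plan does not say whether these count as data.

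There are also safeguards. The trial is double-blind, exclusions are reviewed blind before database lock, and exclusions from the analysis sets are to be described in the clinical trial report. The sets are said to accord with ICH E9, the ITT wording in 17.3 is hedged, and 17.2 links ITT to analysis by randomised arm. The lack of benefit is shown only for the primary imputation. The FAS also serves other analyses, such as the MMRM, which uses post-baseline measurements. Finally, imputing these subjects applies the placebo assumption to them and cannot recover their real outcomes.

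All of this stands, and it limits the weight of the point. None of it supplies a reason for the data condition in the primary analysis. Describing exclusions in the report makes them visible, but it does not show what the estimate would be with those subjects included.

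**Conclusion.** The point holds and is minor. The data condition gains the primary analysis nothing, sits awkwardly with the ITT label, and departs both from the estimand and from the all-randomised basis of the 228. The expected shift is 0.9% of the effect for one excluded liraglutide subject and 4.6% for five, or about 3% and 15% of a standard error. These figures rest on assumed counts, on the planning values in protocol 17.1, and on the excluded liraglutide subjects being ones who would be imputed as placebo. The true count may be zero.

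Four stronger readings are tempting but unsupported:

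- A reader might infer that the randomised comparison is broken or the conclusion at risk. The likely count and the shift are too small for that.
- A reader might infer that bias arises only if early loss is greater on liraglutide than on placebo. Under the plan's assumptions, what matters is the number excluded from the liraglutide arm, whatever happens on placebo.
- A reader might infer that everyone without a post-randomisation BMI SDS is dropped. Dosed subjects with any other post-randomisation data are already in the FAS and already imputed.
- A reader might infer that the sample size must change. It need not, because 228 already assumes that all randomised subjects are analysed.

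**What to change.** For the primary analysis, define the FAS as all randomised subjects, analysed as randomised. This deletes the data condition. It also deletes the one-dose condition, which is likewise post-randomisation and is met almost automatically because the first dose is given on site. State that the added subjects are handled as type MD and that their week 56 value is imputed with the existing placebo-based model. Leave the SAS unchanged. Record the change in SAP section 3, which already lists departures from the protocol, and report by arm how many subjects the present definition would have excluded.

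The sensitivity analyses need little. Added subjects contribute no observations to the MMRM, are not completers, and take their baseline value under BOCF. LOCF needs a stated rule for a subject with no post-baseline BMI SDS, a case that can already arise under the present FAS.

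The cost is a sentence in SAP 2.1, an entry in section 3 and a revised analysis-set flag, settled before database lock. No new data are needed, and N and alpha stay the same. The minimum alternative is to keep the present FAS, add one sensitivity analysis on all randomised subjects, and report exclusions by arm.

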17.3 Primary endpoint

The primary endpoint is change from baseline in BMI SDS after 56 weeks of treatment³³.

The objective is to show that liraglutide is superior to placebo in obtaining weight loss. Let $\mu_{\text{liraglutide}}$ and μ_{placebo} denote the mean change in BMI SDS for liraglutide and placebo, respectively. The null-hypothesis and the alternative hypothesis are:

H0: $\mu_{\text{liraglutide}} = \mu_{\text{placebo}}$ against the alternative HA: $\mu_{\text{liraglutide}} \neq \mu_{\text{placebo}}$

The null-hypothesis will be rejected on a 5% level if the two-sided 95% CI of the treatment difference $\mu_{\text{liraglutide}} - \mu_{\text{placebo}}$ excludes 0. If the upper limit is below 0, superiority of liraglutide against placebo can be concluded.

The hypothesis will be tested using an analysis of covariance (ANCOVA) model with treatment, sex, region, baseline glycaemic category, stratification factor for Tanner stage and interaction between baseline glycaemic category and stratification factor for Tanner stage as fixed effects, and baseline BMI SDS and baseline age as covariates. The baseline glycaemic category includes two levels: presence and absence of dysglycaemia. The stratification factor for Tanner stage includes two levels: stages 2 and 3 together, and stages 4 and 5 together.

Missing data in the main analysis will be handled by the following multiple imputation (MI) method. A pattern mixture model approach is applied where withdrawn subjects without a follow-up visit are assumed to respond as if treated with placebo for the entire trial. Multiple copies (100 copies) of the full dataset will be generated by imputing missing values based on estimated parameters for the placebo group. This will be done as follows:

- In the first step, 100 copies of the dataset will be generated.
- In the second step, an enriched ANCOVA model with sex, region, baseline glycaemic category, stratification factor for Tanner stage and interaction between baseline glycaemic category and stratification factor for Tanner stage as fixed effects and baseline BMI SDS, baseline waist circumference, baseline age and baseline HbA_{1c} as covariates will be fitted to the change from baseline in BMI SDS at 56 weeks for the completers in the placebo group only.
- For each of the 100 copies of the dataset, the estimated parameters and their variances from this model will be used to impute missing values at 56 weeks for subjects in both treatment arms, based on their factor levels and the values of the covariates.
- For each of the 100 complete datasets, the change from baseline in BMI SDS at 56 weeks will be analysed using the main ANCOVA model with treatment, sex, region, baseline glycaemic category, stratification factor for Tanner stage and interaction between baseline glycaemic category and stratification factor for Tanner stage as fixed effects, and baseline BMI SDS and baseline age as covariates.
- The estimates and SDs for the 100 data sets are pooled to one estimate and associated SD using Rubin's formula:

$$m_{MI} = \frac{1}{100} \sum_{i=1}^{100} m_i, SD_{MI} = \sqrt{\frac{1}{100} \sum_{i=1}^{100} SD_i^2 + \left(1 + \frac{1}{100}\right) \left(\frac{1}{100-1}\right) \sum_{i=1}^{100} (m_i - m_{MI})^2},$$

where m_i and SD_i are the estimated means and SDs for the 100 copies of the dataset, and m_{MI} , SD_{MI} are the pooled estimates. From m_{MI} and SD_{MI} , the 95% CI for the treatment difference and the associated p-value will be calculated.

The MI method does not assume missing at random. It assumes that withdrawn subjects in the placebo arm have a response similar to the completers in the placebo arm given similar baseline characteristics. In the active arm, the assumption is that withdrawn subjects behave as if they have been in the placebo arm during the entire trial regardless of the time of their withdrawal. In this way the assumptions are differential and conservative for estimating the treatment effect. The estimate in the primary analysis can be said to be an ITT estimator or an effectiveness estimand of the add-on effect of liraglutide to healthy nutrition and physical activity counselling.

Sensitivity analysis

To investigate the sensitivity of the results of the main analysis of the primary endpoint with regard to the handling of missing data, the following sensitivity analysis will be performed:

- An ANCOVA will be performed with imputation of missing values according to the last observation carried forward (LOCF) method. The model will include terms for treatment, sex, region, baseline glycaemic category, stratification factor for Tanner stage and interaction between baseline glycaemic category and stratification factor for Tanner stage, and baseline BMI SDS and baseline age as covariates. The response variable will be the last available measurement of BMI SDS obtained within the 56-week double-blind period of the trial.
- The same type of ANCOVA as above will be performed, but using an imputation of missing values according to the baseline observation carried forward (BOCF) method. Missing measurements of BMI SDS at 56 weeks will with this method be imputed by the corresponding baseline values.
- The same type of ANCOVA as above will be performed without imputation by only including subjects who completed the 56 weeks double-blind period.
- A mixed model for repeated measurements (MMRM) will be applied where all post baseline BMI SDS measurements obtained at planned visits during the 56-week double-blind period will enter as the dependent variables, and visit, treatment, sex, region, baseline glycaemic category, stratification factor for Tanner stage and interaction between baseline glycaemic category and stratification factor for Tanner stage will be included as fixed effects, and baseline BMI SDS and baseline age as covariates. All these factors and covariates will be nested under visit, which is technically the same as introducing the corresponding interaction terms in the model. An unstructured covariance matrix for the BMI SDS measurements within subject will be employed.

- The ANCOVA model with LOCF assumes that post treatment discontinuation, the body weight is on average stable in both treatment arms. This assumption can be evaluated over the 26 weeks follow-up period in completers. If the assumption holds, the treatment effect (effectiveness estimand) in each arm and the treatment difference can be estimated from this analysis unbiased. If the withdrawal and the development in both arms are similar, the treatment difference can be estimated from this analysis unbiased. If the development in body weight after withdrawal differs between active and placebo, this analysis might provide an optimistic or over-conservative estimate, depending on the actual circumstances. The ANCOVA model with BOCF assumes that post treatment withdrawn subjects return to a body weight in the proximity of their baseline body weight regardless of the timing of withdrawal. This analysis is expected to provide a conservative estimate (effectiveness estimand) of the treatment effect (in each arm). The impact of this assumption on the treatment difference depends on withdrawal pattern over time and development of body weight post withdrawal and reason for withdrawal. The analysis is typically expected to provide a conservative estimate of the treatment difference (effectiveness estimand).
- The MMRM model assumes that withdrawn subjects, had they completed the trial, would not have behaved differently than completing subjects from the same treatment arm with the same baseline characteristics and change in body weight at time of withdrawal. This analysis estimates the treatment effect and difference had all subjects stayed on the randomised treatment (efficacy estimand).
- The ANCOVA analysis in completers is expected to give more positive results than the primary analysis. However, this analysis has its own clinical interpretation and will serve as a benchmark and provide an estimate of the efficacy estimand.

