2.2.1 Sensitivity analysis

To investigate the sensitivity of the results of the main analysis of the primary endpoint about the handling of missing data, a sensitivity analysis will be performed as mentioned below (further details refer protocol section 17.3).

- An ANCOVA will be performed with imputation of missing values according to the last observation carried forward (LOCF) method. The model will include terms for treatment, sex, region, baseline glycaemic category, stratification factor for Tanner stage and interaction between baseline glycaemic category and stratification factor for Tanner stage will be included as fixed effect and baseline BMI SDS and baseline age as covariates. The response variable will be the last available measurement of BMI SDS obtained within the 56-week double-blind period of the trial.
- The same type of ANCOVA as above will be performed but using an imputation of missing values according to the baseline observation carried forward (BOCF) method. Missing measurements of BMI SDS at 56 weeks will be imputed by the corresponding baseline values with this method.

- The same type of ANCOVA as above will be performed without imputation by only including subjects who completed the 56 weeks double-blind period.
- A mixed model for repeated measurements (MMRM) will be applied where all post baseline BMI SDS measurements obtained at planned visits during the 56-week double-blind period will enter as the dependent variables, and visit, treatment, sex, region, baseline glycaemic category, stratification factor for Tanner stage and interaction between baseline glycaemic category and stratification factor for Tanner stage will be included as fixed effects, and baseline BMI SDS and baseline age as covariates. All these factors and covariates will be nested under visit, which is technically the same as introducing the corresponding interaction terms in the model. An unstructured covariance matrix for the BMI SDS measurements within subject will be employed.

For further details refer protocol section 17.3.

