3.1 Primary endpoint

- Primary analysis will be performed on in-trial period.
- Tanner stage and glycaemic category collected at randomisation visit will be considered as fixed effect while performing ANCOVA for change from baseline to week 56.
- Tanner stage for each subject at baseline is been derived and grouped using the information received from eCRF.

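### The MMRM and the completer ANCOVA are labelled as estimating an efficacy estimand, but no rule in the plan keeps off-drug values out of them

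*Protocol*

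**What the plan says.** Protocol 17.3 lists four sensitivity analyses for the primary endpoint and says what each estimates. LOCF and BOCF are tied to an effectiveness estimand. For the MMRM it says: "This analysis estimates the treatment effect and difference had all subjects stayed on the randomised treatment (efficacy estimand"). The completer ANCOVA is also said to give an estimate of the efficacy estimand.

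The MMRM data clause is the same in Protocol 17.3 and SAP 2.2.1: "all post baseline BMI SDS measurements obtained at planned visits during the 56-week double-blind period will enter as the dependent variables". The completer ANCOVA takes subjects who finished the 56-week double-blind period, with no further definition. Neither clause mentions stopping trial product.

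Five other places bear on which values those clauses admit:

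- Protocol 17.2 sets a default: "Data from nominal visits (V19x, V25x and V30x) will be used prior to imputation of remaining missing data unless otherwise stated".
- Protocol 8.1.10 asks subjects who stop trial product early to attend V25x at week 56, and V19x at week 30 if they stopped before V19.
- Protocol 6.5 keeps such subjects in the trial. Only those who refuse further contact count as withdrawn.
- SAP Table 2-2 classes retrieved drop-outs (type AD) as having an available assessment.
- SAP Table 3-1, which is titled as covering scheduled visits, gives V19x and V25x the same target days and windows as V19 and V25 (day 211, window 194 to 225; day 393, window 376 to 400).

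The only on-treatment period in either document is in Protocol 17.4.1.2 and serves adverse events, with a similar rule for hypoglycaemia.

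**The concern.** The effect had everyone stayed on treatment is a hypothetical quantity. A repeated-measures model can target it if values after discontinuation are set aside and the model projects from on-drug data. If off-drug values stay in, the model treats them as ordinary outcomes of the randomised arm, and its target becomes a mixture of on-drug and off-drug response.

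Protocol 17.3 justifies the MMRM only for withdrawn subjects. Under Protocol 6.5, a subject who stops drug but keeps attending is not withdrawn, so the rationale does not cover exactly the subjects who supply off-drug values.

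These are the only two analyses assigned to the efficacy estimand. If both drift toward the effectiveness result, their agreement with the primary analysis could be mistaken for robustness to missing data. The better the retention after discontinuation, the larger the drift. Two programmers working from the same SAP could also produce different efficacy estimates.

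**Working it through.** **Step 1: can an off-drug value reach the model?** A subject stops drug before V19, stays in the trial and attends V25x at week 56. The value lies within 56 weeks of randomisation. Its visit is in the SAP table of scheduled visits. Protocol 17.2 says x-visit data are used unless otherwise stated, and the MMRM clause states nothing else. So nothing written excludes it.

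For the completer ANCOVA, the SAP uses the word completer in more than one way. SAP 2.3.2 imputes from placebo completers, yet describes the same source as types AT+AD and as placebo subjects with BMI SDS at baseline and week 56. That usage includes retrieved drop-outs. SAP 3.2 speaks separately of treatment completers.

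**Step 2: inputs.** All from Protocol 17.1: completer difference -0.26, SD 0.35, 40% withdrawal at week 56, placebo-like response after withdrawal. The 40% is treated here as the share stopping drug, which is an assumption. The share retrieved off drug is not in the documents, so a range is shown.

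**Step 3: reproduce the plan's own figure.**

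- Diluted difference = 0.60 × 0.26 = 0.156.
- Liraglutide-arm SD = √(0.35² + 0.6 × 0.4 × 0.26²) = 0.3725.
- Root-mean-square SD with the placebo arm's 0.35 = 0.3614.
- A two-sided 5% two-sample t-test with 1:1 allocation then needs N = 228 (power 90.06%).

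The same method matches all 18 cells of Table 17-1. The placebo-like assumption used below is therefore the plan's own.

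**Step 4: expected week-56 difference.** Let s be the share of all subjects retrieved off drug, equal in both arms. Then

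difference = -0.26 × 0.60 / (0.60 + s).

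For s = 0.05, 0.10 and 0.20 this is -0.156/0.65, -0.156/0.70 and -0.156/0.80.

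**Step 5: check on a repeated-measures model.** The formula is a cross-sectional average. It suits the completer ANCOVA but not necessarily the MMRM. A likelihood model with unstructured covariance was therefore simulated under these assumptions: visits at weeks 12, 30, 42 and 56; 40% of each arm stopping at random times; placebo-like response off drug; off-drug values only at weeks 30 and 56. Simulation standard errors were 0.001 to 0.004.

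| Retrieved, % of all subjects | % of discontinuers | Formula | Dilution | Simulated model |
|---|---|---|---|---|
| 0 | 0 | -0.260 | 0% | -0.259 |
| 5 | 12.5 | -0.240 | 8% | not run |
| 10 | 25 | -0.223 | 14% | -0.228 |
| 20 | 50 | -0.195 | 25% | -0.199 |
| 30 | 75 | -0.173 | 33% | -0.178 |
| 40 | 100 | -0.156 | 40% | -0.158 |

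With no off-drug values the model recovers the stated estimand. With full retrieval it lands on the diluted 0.156 used for the sample size.

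**Step 6: less discontinuation.** If 20% stop drug, the formula is -0.26 × 0.80 / (0.80 + 0.20r), where r is the share of discontinuers retrieved. It gives -0.245, -0.231 and -0.208 for r = 0.25, 0.5 and 1.

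**The case against.** The strongest reply is that no sentence puts x-visit values into the MMRM. *Planned visits* is undefined. Protocol 8.1.10 calls the x-visits additional, the flowchart gives them separate columns, and SAP Table 3-1 labels them follow-up. The Protocol 17.2 default is worded around imputation, and the MMRM imputes nothing. The LOCF rationale in Protocol 17.3 assumes stable weight after discontinuation, which hints that values from the double-blind period were meant to be on-drug values. Protocol 17.3 also expects the completer analysis to be more favourable than the primary one. All this stands, and it means that exclusion may have been intended. It is not written down, however, and the text that is written points the other way.

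The objection to the size also stands in part. The retrieval shares are assumptions. Read literally under Protocol 6.5, withdrawn subjects could not be retrieved at all. A complete loss of effect off drug is the plan's planning assumption; if part of the effect persists, the dilution is smaller.

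A reader might infer three stronger things that the documents do not support:

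- *That V26 values, two weeks off drug, enter the MMRM.* SAP 3.4.1 does reallocate V26 records in general. But BMI SDS needs height, the height windows in SAP Table 3-2 list no V26, and SAP 3.4.2 lets a collected record displace a reallocated one. No V26 value of BMI SDS is shown to exist. An early V25 is different again: it is taken as soon as possible after stopping and lies close to the last on-drug weight.
- *That SAP 3.1 settles the matter.* "Primary analysis will be performed on in-trial period" names the primary analysis, and SAP 3.2 has a matching line for the secondary ones. Neither names the sensitivity analyses.
- *That the comparison with the primary analysis becomes meaningless.* An MMRM that includes retrieved values would still contrast a same-arm missing-at-random assumption with placebo-based imputation. Its estimand label would be wrong, but it would remain informative about missing-data handling.

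**Conclusion.** The concern holds as a conflict between a stated estimand and the data rules. Protocol 17.3 claims an on-treatment target for the MMRM and an efficacy target for the completer ANCOVA. Neither document restricts the data to match, and the default rules allow V19x and V25x values in. The documents do not prove that these values will be used; they leave it open and lean toward inclusion.

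If the values are used, both estimates shrink toward the effectiveness estimate, by roughly 8% to 25% when 5% to 20% of all subjects are retrieved off drug. This rests on 60% on-drug completers, placebo-like response off drug and equal retrieval in both arms. Under those assumptions the shift is toward the null. The primary analysis, its test of superiority and the sample size of 228 do not change. The point is worth correcting because the correction is cheap and the two analyses have no substitute in the plan.

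**What to change.** Make one of two changes in SAP 2.2.1 before database lock.

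1. **Keep the efficacy label and restrict the data.** State that the MMRM uses only BMI SDS values obtained up to discontinuation of trial product. Count the V25 assessment done at discontinuation as the last on-treatment value when it is taken promptly, with a stated limit in days. Exclude V19x, V25x and any later off-drug record. Define completers as subjects on randomised treatment with a week-56 assessment (type AT in SAP Table 2-2).
2. **Keep the data and drop the efficacy label** from both analyses, describing them as including values after discontinuation.

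Two details matter under the first option. The exclusion should work on assessment date relative to last dose, not on the analysis-visit label. SAP 3.4.1.3 moves BMI SDS records of discontinued subjects to x-visits, so a filter on the label would also remove prompt discontinuation-visit values. The 14-day adverse-event window in Protocol 17.4.1.2 should not simply be borrowed, because it would admit values about two weeks off drug.

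The cost is a few lines of SAP text and the matching data selection. No new data are needed.
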